The etiology of pouchitis remains unclear. There is significant clinical evidence implicating bacteria in the pathogenesis of pouchitis. Studies using culture and molecular methods demonstrate a dysbiosis of the pouch microbiota in pouchitis. The study of ileal pouch mucosal biopsies and fecal samples analyzed with a 16S rDNA-based terminal restriction fragment length polymorphism (TRFLP) approach have revealed statistically significant differences in the mucosal and fecal microbiota between UC and FAP (Familiar adenomatous polyposis) patients who had IPAA (Zella 2011). UC pouches included significantly more TRFLP peaks matching *Clostridium* and *Eubacterium* genera compared to FAP pouches and fewer peaks matching *Lactobacillus* and *Streptococcus* genera compared to FAP. DNA Sanger sequencing of a subset of luminal samples revealed UC pouches having more identifiable sequences of Firmicutes (51.2% versus 21.2%) and Verrucomicrobia (20.2% versus 3.2%), and fewer Bacteroidetes (17.9% versus 60.5%) and Proteobacteria (9.8% versus 14.7%) compared to FAP. Risk factors, genetic associations, and serological markers of pouchitis suggest that the interactions between the host immune responses and the pouch microbiota underlie the etiology of this idiopathic inflammatory condition. Many factors contribute to the course of refractory pouchitis, such as the use of non-steroidal anti-inflammatory drugs, infection with *Clostridium difficile*, pouch ischemia, or concurrent immune-mediated disorders.

Initial acute episodes typically respond to antibiotic therapy such as metronidazole, patients can become dependent on antibiotics or develop refractory disease. Different treatments for the refrac-

tory pouchitis have been tested including different treatments used in the treatment of UC (mesalazine, immunosuppressive or immunomodulative), but long term remission is seldom achieved. Probiotics, especially products containing many strains of probiotics such as VSL3# have been effective in some studies (Gionchetti 2003). Otherwise a single-strain probiotic bacterium supplement of Lactobacillus GG has been shown to be ineffective (Kuisma 2003).

Treatment of recurrent *Clostridium difficile*-infection (CDI) with antibiotics leads to recurrences in up to 50% of patients. It has been shown that fecal microbiota transplantation (FMT) through colonoscopy is an effective treatment for recurrent CDI in over 90% of CDI patients. Transplantation was done for 70 patients and no significant complications occurred for the transplantation procedure (Mattila 2012). Case reports have also shown promising results of FMT in IBD patients (Anderson 2012). Only one case report about FMT in the treatment of *Clostridium difficile*-associated pouchitis is available (Patel 2013), where a patient with chronic antibiotic-dependent pouchitis contracted refractory CDI. FMT lead to the eradication of CDI, but the baseline chronic pouchitis remained. There are three prospective uncontrolled cohort studies and one case report about FMT in the treatment of chronic pouchitis, reporting on 23 patients in total. Two of the cohort studies used a single FMT infusion with 25% (2/8) achieving clinical response in one study (Landy 2015) and 71% (5/7) in the other study (El-Nachef 2016), but no patients achieved clinical remission. In the third cohort study was used multiple FMT infusions and 4 of 5 patients achieved clinical remission and the other patient achieved clinical response (Stallmach 2016). The only case report used single infusion and the patient achieved clinical remission (Fang 2016).

Currently there is no established effective treatment for chronic antibiotic dependent or refractory pouchitis. The aim of our study is to investigate the efficacy and safety of fecal transplantation in treatment of chronic pouchitis instead of antibiotic therapy. Another aim is to evaluate phylogenetic analysis of the fecal microbiota trying to find microorganisms contributing to good results in fecal transplantation in IPAA patients.

STUDY DESIGN

STUDY POPULATION

Inclusion criteria for study

- Status post of restorative proctocolectomy with ileal pouch-anal anastomosis (IPAA) for ulcerative colitis
- Pouchitis diagnosed by the symptoms and by endoscopy including histology within 6 months prior to FMT.
- Need of frequent or continuous use of antibiotics or probiotics because of the chronic pouchitis
- Availability of consecutive fecal samples during one year
- Compliance to attend FMT and control pouchscopy after 52 weeks
- 18-75 years

Exclusion criteria for study

- Unable to provide informed consent
- Use of immunosuppressive or biological medication
- Pregnancy

METHODS

26 consecutive patients with pouchitis diagnosed by the symptoms and endoscopy. Patients are collected from the Helsinki University Central Hospital. Use of antibiotics or probiotics is not continued during the study. Fecal microbiota transplantation (FMT) is performed by experienced endoscopists using frozen and thawed stool through flexible sigmoidoscopy into the afferent limb. The second FMT is installed via catheter into the pouch 3 weeks after the first FMT. Antibiotic treatment has been stopped 36 hours before the FMT. 13 pouchitis patients receive a fecal transplantation from the healthy tested donor and 13 patients in the control group receive their own feces donated and prepared at the same day. The endoscopists and personnel performing the FMT are blinded for the type of feces. The randomization is done by a doctor not attending the study. Pouchscopy is assessed at 52 weeks to evaluate the endoscopic and mucosal healing. Clinical Pouchitis Disease Activity Index, see table 1 (Sandborn 1994) is assessed at week 4, 12, 26 and 52 and in addition to the endoscopy and histological index at weeks 0 and 52.

Table 1 Pouchitis Disease Activity Index (Sandborn 1994).

Table 1.
The Pouchitis Disease Activity Index⁴

Criteria	Score
Clinical	
Stool frequency	
Usual postoperative stool frequency	0
1–2 stools/day > postoperative usual	1
3 or more stools/day > postoperative usual	2
Rectal bleeding	
None or rare	0
Present daily	1
Fecal urgency or abdominal cramps	
None	0
Occasional	1
Usual	2
Fever (temperature > 37.8° C)	
Absent	0
Present	1
Endoscopic inflammation	
Edema	1
Granularity	1
Friability	1
Loss of vascular pattern	1
Mucous exudates	1
Ulceration	1
Acute histologic inflammation	
Polymorphic nuclear leukocyte infiltration	
Mild	1
Moderate + crypt abscess	2
Severe + crypt abscess	3
Ulceration per low-power field (mean)	
>25%	1
25–50%	2
>50%	3

Donors are excluded if they have taken antibiotics within the preceding 3 months; are on immunosuppressive or chemotherapeutic agents; have known or recent exposure to HIV; hepatitis B or C; have a current communicable disease; are morbidly obese; have IBD, IBS, atopy, chronic diarrhea or constipation; GI malignancy or polyposis; participate in high-risk sexual behaviors; use illicit drugs; have a history of recent incarceration or travel to areas with endemic diarrhea. Donor

blood testing includes tests for HIV, hepatitis A, B and C; donor stool testing includes culture, *C. difficile* toxin, ova and parasites, and *Helicobacter pylori*.

Follow up of the patients include a telephone call after 12 and 26 weeks after the FMT, and a clinical control visit 52 weeks after the transplantation. The clinical part of the Pouchitis Disease Activity Index score is assessed during each call and clinical visit.

A general quality of life measurement (15D-questionnaire, www.15d-instrument.net) is done at the day of stool transplantation and 6 months after the transplantation. Any adverse events are recorded. Changes in the use of medication is recorded.

Fecal stool samples for phylogenetic analysis are collected before FMT and on weeks 4, 12, 26, and 52. Fecal calprotectin indicating level of inflammation is measured before FMT and on weeks 4, 12, 26 and 52.

Endpoint of the study is the remission defined as Pouchitis Disease Activity Index <7 and no need for antibiotic treatment of pouchitis during the 52-week follow-up. Secondary objective for this study include an evaluation of the changes in gut microbiota within the 52 weeks.

STATISTICAL ANALYSIS

The sample size is calculated in according to the estimation that the difference in remaining in remission is 55% (80 vs 25%) over 52 weeks. The calculated sample size is 26 patients and therefore 13 patients are selected for both groups (donor vs own feces). This difference is considered to be clinically meaningful. Confidence interval was selected to be 95% ($\alpha=0.05$ and $\beta=0.1$).

DATE

Patient collection will be made from September 2017 until June 2018. The follow up of the patients will end one year after the last patient included the study. Data analysis and reporting of the results will be during the year 2019.

ETHICAL ASPECTS

The possible ethical risks for this study include the possible transmission of harmful microbiota to the patients causing some infection or other diseases. The risk is most likely minimal, because the feces and the donors are widely tested for many known pathogens and diseases. Risk for the activation of pouchitis is also possible, although this is unlikely according to previous case reports about FMT in IBD. All the patients are informed about the experimental nature of this treatment procedure and about the available results in other previously published reports and possible risks of the procedure. All of the patients are asked for informed consent. The permission for this study will be appealed from the Institutional Review Board of Helsinki University Central Hospital.

WHAT MAKES THIS RESEARCH INNOVATIVE

This is the first placebo controlled study of fecal transplantation in pouchitis patients. The study of microbiota by the repeated fecal samples during the one year follow-up makes it possible to study if the change in the gut microbiota is permanent after the fecal transplantation.

REFERENCES

Abreu MT. Toll-like receptor signaling in the intestinal epithelium: how bacterial recognition shapes intestinal function. *Nat Rev Immunol* 2010;10:131-44.

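### Table 1, histologic ulceration: the 1-point row, as read, is >25%, which overlaps both higher rows and leaves ulceration below 25% unscored; probably a reversed sign, to be checked against the printed page

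*Combined protocol and SAP*

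**What the plan says.** METHODS introduces the scoring instrument as "Clinical Pouchitis Disease Activity Index, see table 1" and attributes it to a 1994 publication. In Table 1, under acute histologic inflammation, the item "Ulceration per low-power field (mean") has three rows as read: >25% scores 1, 25–50% scores 2 and >50% scores 3. The table has no row for ulceration below 25% and no rule for a value that fits two rows. Nothing elsewhere in the document restates or corrects the item.

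On timing, METHODS has the clinical index assessed at weeks 4, 12, 26 and 52, "in addition to the endoscopy and histological index at weeks 0 and 52". For follow-up contacts it adds: "The clinical part of the Pouchitis Disease Activity Index score is assessed during each call and clinical visit". Week 52 is therefore the only follow-up time at which histology enters the score.

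The endpoint, at the end of METHODS, has two conditions: "remission defined as Pouchitis Disease Activity Index <7" and "no need for antibiotic treatment of pouchitis during the 52-week follow-up".

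**The concern.** The points ascend 1, 2, 3, so the bands should ascend with them and should not overlap. As read they do neither. Any ulceration above 25% fits the 1-point row and also a higher row, while ulceration above zero and below 25% fits none.

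The item contributes to the week-52 total, which is judged against a fixed cut-off of 7. A scoring error of a single point can therefore move a patient across the line between remission and no remission. Week 0 matters only for consistency, because the inclusion criteria ask for symptoms and endoscopy including histology and set no cut-off on the index.

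**Working it through.** The plan gives no derived figure for this item, so there is none to reproduce first. The sample size of 26 does not depend on it.

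**Inputs (METHODS, Table 1).** Maximum scores of the other items:
- clinical: 2 + 1 + 2 + 1 = 6
- endoscopic: six features at 1 point each = 6
- leukocyte infiltration: 3

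Let O be the total of all items except ulceration. O runs from 0 to 6 + 6 + 3 = 15, and the whole index runs to 15 + 3 = 18.

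**Assumptions.** A finding that matches no row scores 0. The comparison reading has exclusive, ascending rows: present but below 25% = 1, 25–50% = 2, above 50% = 3. It serves to test sensitivity.

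**Rule for a change in status.** Let L be the literal score and E the score under exclusive rows. L is never above E. Scores are whole numbers, so status differs when O + L ≤ 6 and O + E ≥ 7, that is, when 7 − E ≤ O ≤ 6 − L.

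| Ulceration | Rows matched as read | L used | E | Condition on O | Totals, literal vs exclusive |
|---|---|---|---|---|---|
| Above 0, below 25% | none | 0 | 1 | 6 ≤ O ≤ 6 | 6 vs 7 |
| Exactly 25% | 2-point | 2 | 2 | 5 ≤ O ≤ 4 | no change |
| Above 25%, up to 50% | 1- and 2-point | 2 | 2 | 5 ≤ O ≤ 4 | no change |
| Same | same | 1 | 2 | 5 ≤ O ≤ 5 | 6 vs 7 |
| Above 50% | 1- and 3-point | 3 | 3 | 4 ≤ O ≤ 3 | no change |
| Same | same | 1 | 3 | 4 ≤ O ≤ 5 | 5 vs 7; 6 vs 8 |

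**Reading the table.** If a scorer always takes the highest matching row, only the first line changes status: ulceration present but below 25% and O exactly 6. The cases at O = 5, and at O = 4 or 5, need a scorer to choose 1 point although an explicit higher row fits. If the scorer infers from the ascending order that 1 point means below 25%, nothing changes.

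**Second endpoint condition.** A change in the index changes the endpoint only in a patient who also had no need for antibiotics during follow-up. A patient who needed them is not in remission on either score.

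**Scale.** Each arm has 13 patients, so one reclassified patient would move that arm's remission proportion by 1/13 = 7.7 percentage points. The document gives no distribution of scores, so the number of such patients cannot be estimated.

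**The case against.** The point rests on one character in a table that was read by a program. Other signs in the table read sensibly, for example "Fever (temperature > 37.8° C") and "3 or more stools/day > postoperative usual", but they do not settle the matter. The suspected misreading is of < as >, and the table contains no < that would test it. The < in the endpoint sentence is in running text. The table also looks copied from elsewhere: it has two captions, and its title carries a superscript 4 although the reference list is unnumbered. The error could lie in the source, in the copying or in the extraction. This objection stands, and it is why confidence is low.

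Scorers may have worked from the cited index and not from this reproduction. That is possible, but METHODS sends the reader to Table 1, so the row is worth verifying.

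The other two rows leave only one band for 1 point, and most scorers would infer it. This stands too. It disposes of the overlap cases for any scorer who honours the explicit higher rows. It closes the gap below 25% only by an inference that the table does not state.

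From the overlap, a reader might infer that several patterns of scores produce false remissions, or that the comparison of donor with own feces is biased. The document supports neither. The overlap patterns require passing over an explicit higher row. Every change in the working is towards remission, but only relative to the assumed exclusive reading, and the same rows apply to both arms.

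**Conclusion.** The point holds in a narrow, conditional form. As read, Table 1 is internally inconsistent in one row of the instrument that defines the endpoint, and a reversed sign is the likeliest explanation. If it is printed that way and followed literally with the highest matching row, the exposure is limited to patients who meet three conditions at week 52: ulceration present but below 25%, other items totalling exactly 6, and no need for antibiotics during follow-up. Their number is unknown and may be zero.

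The conclusion assumes that the extracted sign matches the printed page, that the scorers used this table, and that a finding without a row scores 0. If the sign was misread, the point lapses. It should not be read as an error in a calculation of the plan, as evidence that any patient was misclassified, or as a reason to revisit the sample size. It is a minor correction, held with low confidence.

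**What to change.** Check the 1-point ulceration row against the original page of the protocol and against the index it cites. If the printed sign is already <, no change is needed. If the row is printed as >25%, reconcile it to <25% (present but below 25%), the only band left by the 25–50% and >50% rows. Then confirm that the week-52 ulceration scores were assigned with the corrected rows; week 0 can be checked at the same time for consistency.

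The cost is one table row and a check of at most 26 week-52 scores. Design, sample size and visit schedule are unaffected.

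### Do antibiotic use and treatment arm confound the search for organisms linked to remission, so that the plan needs a rule for both?

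*Combined protocol and SAP*

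**What the plan says.** The introduction names, as a second aim, a search for microorganisms behind a good response to FMT. The METHODS section gives the sampling: "Fecal stool samples for phylogenetic analysis are collected before FMT and on weeks 4, 12, 26, and 52". It states the secondary objective only as an evaluation of change in gut microbiota over the 52 weeks. The inclusion criteria ask for "Availability of consecutive fecal samples during one year", and no passage makes sampling conditional on antibiotic use.

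The endpoint is a Pouchitis Disease Activity Index (PDAI) below 7 together with "no need for antibiotic treatment of pouchitis during the 52-week follow-up". On follow-up, "The clinical part of the Pouchitis Disease Activity Index score is assessed during each call and clinical visit"; the full index is scored "in addition to the endoscopy and histological index at weeks 0 and 52". On medication the plan says "Changes in the use of medication is recorded".

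STATISTICAL ANALYSIS contains only the sample size, based on the estimate that "the difference in remaining in remission is 55% (80 vs 25%) over 52 weeks". It names no microbiota comparison, time point, arm adjustment or handling of samples taken after antibiotics are restarted.

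**The concern.** Antibiotics are built into failure, and they alter gut flora. A sample taken after a restart comes from a patient who has already failed, so a taxon suppressed by antibiotics would look like a marker of remission. Arm acts in the same way: most remitters are expected in the donor arm, so any organism carried over in donor stool would be commoner among remitters whether or not it does anything.

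A related worry is the baseline. Some patients will have been on antibiotics until shortly before FMT, so change from the pre-FMT sample within one arm may include recovery from antibiotics. The section WHAT MAKES THIS RESEARCH INNOVATIVE presents permanence of the microbiota change as a selling point, and a reading of one arm alone could mistake that recovery for a lasting effect.

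At stake is a false report that a given organism explains success. The primary endpoint is not touched.

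**Working it through.** **Planning inputs.** STATISTICAL ANALYSIS gives 80% and 25% remission, 13 per arm, α = 0.05, β = 0.1. With the two-sided unpooled formula, n per arm = (1.960 + 1.282)² × (0.80 × 0.20 + 0.25 × 0.75) / 0.55² = 10.51 × 0.3475 / 0.3025 = 12.07, rounded up to 13, or 26 in total. The plan's figure is reproduced.

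**Route to failure before week 52.** The clinical items in Table 1 have maxima 2 + 1 + 2 + 1 = 6, below the threshold of 7. On the scheduled assessments, failure before week 52 can only be antibiotic need. This does not say how many failures occur early: a PDAI of 7 or more at week 52 without antibiotics is also failure. The share exposed at any given sample is therefore unknown.

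**Outcome by arm.**

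| | Donor | Own feces | Total | Donor share |
|---|---|---|---|---|
| Remitters | 13 × 0.80 = 10.4 | 13 × 0.25 = 3.25 | 13.65 | 76% |
| Non-remitters | 13 × 0.20 = 2.6 | 13 × 0.75 = 9.75 | 12.35 | 21% |

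**What a pooled test would do.** Simulation of 40,000 trials with 13 per arm, remission drawn at the planning rates, normal log-abundance and one taxon with no role in remission. Assumed, not from the documents: each failure is exposed at the sample with probability f of 0.25 or 0.5, exposure lowers the taxon by 1 SD, and donor stool raises it by 1 SD. Share of trials significant at nominal 5%:

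| Analysis | f = 0.25 | f = 0.5 |
|---|---|---|
| Pooled, antibiotics only | 8.6% | 20.3% |
| Pooled, arm only | 24.3% | 24.3% |
| Pooled, both sources | 41.4% | 60.5% |
| Both sources, exposed samples dropped | 21.3% | 17.3% |
| Both sources, stratified by arm | 7.4% | 15.5% |
| Both sources, both corrections | 5.0% | 5.1% |

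**What the double correction costs.** Samples left are 13 − f × failures: at f = 0.25, 10.56 own-feces and 12.35 donor; at f = 0.5, 8.13 and 11.70. Unexposed donor-arm failures are 2.6 × (1 − f) = 1.95 or 1.3. Their number is binomial with 13 patients and probability 0.20 × (1 − f) = 0.15 or 0.10:

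- none: 0.85¹³ = 12%, or 0.90¹³ = 25%;
- one or none: 12% + 13 × 0.15 × 0.85¹² = 40%, or 25% + 13 × 0.10 × 0.90¹² = 62%.

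Power for a true 1 SD remission difference falls from 49% with no exposure to 43% or 35%.

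The 5% in the last row of the table holds because exposure was drawn at random among failures. If failures with below-average levels of the taxon are four times as likely to restart antibiotics (assumed), the same analysis is significant in 5.6% or 11.7% of trials. A taxon lowered 1 SD by active inflammation, a consequence of failing, is flagged in 43% or 34%, about as often as a true cause.

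**Within-arm change.** With 13 patients, a within-patient correlation of 0.5 and a quarter to a half of baselines lowered by 1 SD (all assumed), a paired test with no FMT effect is significant in 11.4% to 31.4% of trials. The donor-versus-own comparison of change stays at 5.1% and 4.8%.

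**The case for a change.** The best case for a change is that the aim in the introduction cannot be met without relating microbiota to outcome, and the plan leaves the most confounded version open. Neither correction alone suffices across the assumed range. The remedy would be a few sentences, plus start and stop dates in a medication record that is already kept. Calling the aim exploratory does not stop a spurious organism from being published.

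The structure of that argument stands: the link of both antibiotics and arm to outcome follows from the plan's own endpoint and rates, and no rule is written. Three things weaken it. First, the error rates belong to a pooled, unadjusted, single-taxon test that the plan does not propose. The aim can equally be read as a question within the donor arm, where confounding by arm cannot arise, and with many taxa neither these error rates nor these powers describe a real report. Second, the proposed rule exchanges one bias for another: dropping exposed samples selects on an event after randomisation that is tied to failure, and stratifying by arm discards the signal from organisms that donor stool transfers, a plausible route to benefit. Third, the statement that antibiotics are not continued during the study need not conflict with the endpoint. It can be read as ending existing use, while the endpoint counts a later need. What is unstated is only how samples after a restart are treated.

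**Conclusion.** No change follows. This is a gap that analysts can fill sensibly. No rule stated in the plan gives a wrong result: the formal secondary objective can be answered by the randomised contrast in all patients, which neither antibiotic exposure nor arm biases when it is read as the effect of assignment. Any outcome-linked result from 26 patients can only generate hypotheses, and the recorded medication changes let analysts show it by arm, with and without exposed samples, provided dates are in the record.

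The potential distortion in a naive pooled test is large, 41% to 60% against a nominal 5%, but that range rests wholly on the assumed exposure share and 1 SD shifts; the documents give neither. Fixing the double correction in advance would not buy assured error control, and it would leave about 1.3 to 1.95 expected donor-arm failures to carry a question about why FMT works.

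### Between the transplant and week 52, only need for antibiotics can fail the remission endpoint; a probiotic or other rescue drug does not count, and the interim clinical score cannot reach the cut-off

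*Combined protocol and SAP*

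**What the plan says.** METHODS gives the endpoint as "remission defined as Pouchitis Disease Activity Index <7 and no need for antibiotic treatment of pouchitis during the 52-week follow-up". It has a score component and a drug component, and the sentence does not say at which visit or visits the score must be below 7.

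On timing, METHODS says that the clinical index "is assessed at week 4, 12, 26 and 52 and in addition to the endoscopy and histological index at weeks 0 and 52". The follow-up paragraph confirms this: "The clinical part of the Pouchitis Disease Activity Index score is assessed during each call and clinical visit". The contacts at weeks 12 and 26 are telephone calls, and the only planned pouchscopy after FMT is at week 52.

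On drugs, one inclusion criterion is "Need of frequent or continuous use of antibiotics or probiotics because of the chronic pouchitis". METHODS then says: "Use of antibiotics or probiotics is not continued during the study". Changes in medication are recorded, but only antibiotics appear in the endpoint. Immunosuppressive or biological medication is an exclusion criterion; the text does not say what follows if such a drug is started later.

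The background names non-antibiotic options. It states: "Probiotics, especially products containing many strains of probiotics such as VSL3# have been effective in some studies". It also lists "different treatments used in the treatment of UC (mesalazine, immunosuppressive or immunomodulative" among the therapies tried for refractory pouchitis, and adds that lasting remission with them is rare.

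STATISTICAL ANALYSIS bases the sample size on the estimate that "the difference in remaining in remission is 55% (80 vs 25%) over 52 weeks".

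**The concern.** The planning figures concern staying in remission for a year. Between FMT and week 52 the endpoint rule registers one thing only: whether antibiotics were needed. The plan gives no criterion for need, so classification in that period rests on clinical discretion.

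The drug component is also narrower than the entry criterion. Need for antibiotics or probiotics qualifies a patient, but only need for antibiotics fails one. A patient can enter because of probiotic need, go back to a probiotic after FMT, score below 7 at week 52 and be counted as a success of the assigned treatment. The same holds for any other pouchitis drug started during follow-up.

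If such patients were equally common among the failures of both arms, the observed difference would shrink. If they were more common in one arm, the bias could go in either direction.

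**Working it through.** **1. Can the interim score reach the cut-off?** Inputs: clinical items of Table 1.

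| Item | Range |
|---|---|
| Stool frequency | 0–2 |
| Rectal bleeding | 0–1 |
| Urgency or cramps | 0–2 |
| Fever | 0–1 |

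Maximum = 2+1+2+1 = 6. Possible combinations = 3×2×3×2 = 36, and none reaches 7. The endoscopic part adds up to 6 and the histologic part up to 6, so the full index runs to 18, but it is available only at weeks 0 and 52.

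**2. Both readings of the score component.** If PDAI <7 applies at every assessment, it is met automatically at weeks 4, 12 and 26. If it applies only at week 52, the interim scores play no part. On either reading, only antibiotic need can fail a patient before week 52.

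**3. Treatment paths under the rule as written**, each for a patient with total PDAI <7 at week 52:

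| Event during follow-up | Classified as |
|---|---|
| Antibiotics needed | Failure |
| Probiotic restarted | Remission (also a protocol deviation) |
| Another pouchitis drug started | Remission |
| Flare settles, antibiotics not judged needed | Remission |

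A flare that persists to week 52 can still fail on the full PDAI.

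**4. The plan's sample size.** Inputs from STATISTICAL ANALYSIS: 80% vs 25%, α = 0.05, β = 0.1. The sidedness and the formula are not stated. The unpooled two-sided formula gives

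n = (1.960+1.282)² × (0.80×0.20 + 0.25×0.75) / 0.55² = 10.507 × 0.3475 / 0.3025 = 12.07,

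which rounds up to 13 per arm, or 26 in total. The stated figure reproduces.

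**5. Illustration of sensitivity.** Assumption, not in the documents: 80% and 25% are rates under a stricter outcome, and a share q of the failures in each arm is counted as remission. The donor rate becomes 0.80+0.20q, the own-feces rate 0.25+0.75q, and the difference 0.55(1−q). Power is by exact enumeration with 13 per arm, two-sided 0.05. The plan names no test, so two are shown.

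| q | Donor vs own | Difference | Power, uncorrected chi-square | Power, Fisher |
|---|---|---|---|---|
| 0 | 80.0% vs 25.0% | 55.0 points | 89% | 79% |
| 10% | 82.0% vs 32.5% | 49.5 points | 82% | 68% |
| 20% | 84.0% vs 40.0% | 44.0 points | 72% | 56% |
| 30% | 86.0% vs 47.5% | 38.5 points | 61% | 44% |

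At q = 20% the expected number misclassified is 13×0.75×0.2 = 1.95 own-feces patients and 13×0.20×0.2 = 0.52 donor patients. If 20% applied in one arm only, the difference would be 80−40 = 40 points (own feces only) or 84−25 = 59 points (donor only).

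In counts, 10/13 vs 3/13 is a difference of 54 points (95% Newcombe interval 15 to 75; Fisher p = 0.017). Moving two own-feces patients to remission gives 10/13 vs 5/13, or 38 points (1 to 64; Fisher p = 0.11, chi-square p = 0.047).

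**The case against.** The strongest case for the plan is that PDAI <7 at week 52 without antibiotics is a legitimate endpoint. It matches the stated aim of using FMT in place of antibiotics, and on that reading the interim scores are simply descriptive. This stands. A reader might infer that every interim flare ought to fail the primary endpoint. The documents do not support that: entry itself required symptoms plus endoscopy with histology, so a symptom score taken by telephone does not establish a relapse. The change proposed here also leaves an untreated flare that settles as remission in the primary analysis.

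Second, the plan says need, not use. A patient judged to need antibiotics fails even if none are given, so it would be wrong to say that only a prescription counts. What remains is that need is undefined.

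Third, the non-antibiotic routes look narrow. Probiotic rescue departs from the protocol, and immunosuppressives and biologics are excluded at entry. The background says that the other drugs seldom bring lasting remission, and the probiotic study it cites concerned, by its title, prevention of pouchitis onset. This lowers the likely frequency. It does not settle how such a patient is classified: a deviation has no stated consequence for the endpoint, and the exclusion is not extended past entry.

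Fourth, 80% and 25% may already be rates of the endpoint as written, since they follow directly on its definition. In that case the dilution in the illustration does not arise. This objection also stands.

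**Conclusion.** The concern holds in a limited form and is minor. Three facts come straight from the documents: the interim clinical score cannot reach 7, only antibiotic need can fail a patient before week 52, and a patient rescued with a probiotic or another pouchitis drug who scores below 7 at week 52 is counted as in remission.

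The size is unknown. A reader might take the power table as showing that the trial is underpowered because of this rule. It does not: q is assumed, and so is the reading of 80% and 25% as rates of a stricter outcome. The count example shows only that, with 13 per arm, two patients can move a Fisher result across 0.05, while the uncorrected chi-square stays just below it.

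Nor should a reader infer that flares go unrecorded. Clinical scores, calprotectin, adverse events and medication changes are all collected, and the week-52 clinical score and any antibiotic restart already bear on the endpoint. The gap is that the rule ignores non-antibiotic treatment and makes no use of the interim scores.

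**What to change.** 1. Define remission as total PDAI <7 at week 52 **and** no antibiotic (needed or given), probiotic or other new drug treatment for pouchitis from the first FMT to week 52. Classify the drug component from the medication changes already recorded.
2. Add one prespecified sensitivity analysis that also counts as failure a symptomatic flare at week 4, 12 or 26. Define the flare by a threshold on the 0–6 clinical scale, supported by calprotectin, and fix it before unblinding. The documents give no threshold, so the sponsor must choose one.

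The cost is one rewritten endpoint sentence and one extra analysis. The scores, calprotectin and medication records are already scheduled, and no new sample size is proposed. There are three downsides: remission may be somewhat lower in both arms, probiotic use depends on patient report, and the flare threshold is a judgement.
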